4.3 Process for Obtaining Informed Consent

Prior to undergoing any study-specific tests or procedures, the subject must sign and date the site's current and approved Institutional Review Board (IRB) informed consent from to be eligible for study participation. The informed consent must contain all elements required by 21 CFR Part 50 and ISO 14155:2011/AC:2011 and comply with the ethical principles of the Declaration of Helsinki.

4.3.1 Process for Obtaining Informed Consent

The patients will be informed by the Investigator or Investigator's designee that they are free to refuse participation in this research study. If they elect to participate, it will be made clear that they may withdraw from the study at any time without prejudicing further care.

The Investigator or the Investigator's designee will inform patients that their medical records will be subject to review by the sponsor or appropriate regulatory bodies. This information will be used during the analysis of the results of the clinical study, but the patients' identities will be treated as confidential. Patients will be assigned a unique study subject code that will not reveal the patients' identity, and this code will be used on all data and data collection forms during the study period. The Investigator will explain the conditions of the study, giving the patient sufficient time to ask questions and to consider whether to participate. Eligible patients who agree to participate will be asked to sign and date an IRB approved informed consent. If the patient agrees, an IRB approved consent form will be provided to the patient for signature and date. One copy shall be returned to the Investigator and filed in the patient's case history; the other copy is for the patient to keep.

4.3.2 Addition of New Information

Pulse Biosciences, Inc. will revise the written informed consent form whenever new information becomes available that may be relevant to the subject's confirmed participation in the study. The revised information will be sent to the Investigator for approval by the IRB. After approval of the IRB, a copy of this information must be provided to the participating subjects, and the informed consent process as described above needs to be repeated. Please follow the central IRB guidelines on the process of re-consenting subjects.

4.4 Schedule of Events and Evaluations

Schedule of events and evaluations required for this study are provided in **Table 3**.

Table 3. Schedule of Events

Study Activity/ Procedure	Visit 1 Screening/ Enrollment & Tx	Visits 2-4 3, 7, 14-days Post-Tx	Visits 5 30-days Post-Tx	Visit 6 Excision (60-days Post-Tx)	Visit 7 14-days Post Excision	Visit 8 30-days Post Excision	Visit 9 60-days Post Excision
Study Day	0	3/7/14	30	60	74	90	120
Visit Window	Day 0	±2 days	±5 days	±5 days	±3 days	±5 days	±5 days
Type of Visit							
OV – In-Office Visit Required OV/TM – In-Office Visit or Telemedicine Visit	OV	Visit 2 & 3: OV/TM Visit 4: OV	OV/TM	OV	OV	OV/TM	OV
Inclusion/Exclusion Informed Consent	✓						
Demographics, Medical HX, Fitzpatrick Skin Type, etc.	✓						
Lesion History	✓						
History of Pigmentary Changes	✓						
Photographs	✓ a	✓ * ✓ *	✓ * ✓ *	✓ a ✓ a	✓ a ✓	✓ * ✓ *	✓ ✓
Lesion Assessment (Investigator)	✓ a	✓ * ✓ *	✓ * ✓ *	✓ a ✓ a	✓ ✓	✓ * ✓ *	✓ ✓
Tattoo Treatment Area	✓						
CellFX Treatment	✓						
Procedural Pain Assessment (Subject)	✓			✓			
Surgical Excision				✓			
Suture Removal (as applicable)					✓		
SCAR-Q Appearance Scale (Subject)				✓ b ✓ b			✓ ✓
Manchester Scar Scale (Investigator)				✓ b ✓ b			✓ ✓
Healing Assessment Questions (Investigator)				✓ b ✓ b			✓ ✓
Lesion Measurement	✓			✓ b ✓ b			
Clinical Clearance Assessment				✓ b ✓ b			
Adverse Events	✓	✓ ✓	✓ ✓	✓ ✓	✓ ✓	✓ ✓	✓ ✓
Study Exit							✓

^a Pre- and post-procedure / Surgical Excision / Suture Removal

^b Pre-procedure / Surgical Excision

* Required for in-office visits only

4.5 Screening / Enrollment Procedures (Visit 1)

The following activities are required at the time of the subject screening/enrollment visit. The order of the activities may vary within reason as long as all activities are performed after consent is obtained. The Screening Visit and Treatment Visit (subject enrollment visit) may occur on different days.

4.5.1 Activities prior to or on same day as study enrollment

- Evaluation for Inclusion/Exclusion criteria.
- Collect Demographic information and medical history including but not limited to age, gender, race, ethnicity, dermatologic conditions, and Fitzpatrick skin type.
- Sign the consent form prior to any study activities.
- Receive a copy of the signed consent form.

All screening evaluations must be completed and reviewed to confirm that potential participants meet all eligibility criteria. Procedures conducted as part of the participant's routine clinical management and obtained before signing of the ICF may be utilized for screening or baseline purposes provided the procedures met the protocol-specified criteria.

4.5.2 Definition of Enrollment

Once the subject has been consented and has received a CellFX treatment, the subject will be considered enrolled and each enrolled subject will be assigned a unique Study Identification Number.

4.5.3 CellFX Treatment Procedure

- 1-2 clinically diagnosed BCC lesion(s) that meet the study criteria will be selected by the treating investigator. The identified lesion(s) will be labeled.
- Baseline photographs will be taken (prior to use of analgesic for pain management and prior to tattooing).
- Baseline clinical measurements of the BCC lesion(s) shall be taken
- The site investigator will perform a baseline lesion(s) assessment.
- A template will be applied to the skin and used to map out the treatment application.
- A tattoo (4 marks) will be applied within the area designated for excision to mark the treatment zones for the purpose of identifying the treatment area during evaluation.
- An analgesic for pain management, such as local injection of lidocaine, will be administered to the selected study lesion area(s).
- Each study lesion will be treated with the CellFX system per Table 2 according to the treatment tips utilized.
- The total number of treatment cycles with the CellFX system will be recorded.
- The subject will be asked to rate his/her pain immediately after the treatment session for each lesion treated with the CellFX system by using a numerical rating score, depicted in Figure 4.
- Post-procedure lesion assessment will be performed by the investigator.
- Post-procedure photographic images of each selected lesion will be taken.
- A light bandage and/or any physician recommended dressing may be applied before the subject leaves.
- Any adverse events will be identified and documented.

4.6 3-Day Follow-up Visit (Visit 2)

- This visit may be performed in-office or as a telemedicine visit.
- Photographic images of each study lesion will be taken. Photographs are not required if the visit is not performed in-office.
- All lesions will be examined and clinically assessed by the site investigator. If the visit is not performed in-office, clinical assessment is not required.
- A light bandage and/or any physician recommended dressing may be applied post-evaluation.
- Any adverse events will be identified and documented. If the visit is not performed in office, the clinical site must inquire regarding any adverse events either by phone call, text, e-mail or video conference.

4.7 7-Day Follow-up Visit (Visit 3)

- This visit may be performed in-office or as a telemedicine visit.
- Photographic images of each study lesion will be taken. Photographs are not required if the visit is not performed in-office.
- All lesions will be examined and clinically assessed by the site investigator. If the visit is not performed in-office, clinical assessment is not required.
- A light bandage and/or any physician recommended dressing may be applied post-evaluation.
- Any adverse events will be identified and documented. If the visit is not performed in office, the clinical site must inquire regarding any adverse events either by phone call, text, e-mail or video conference.

4.8 14-Day Follow-up Visit (Visit 4)

- Photographic images of each study lesion will be taken.
- All lesions will be clinically assessed by the investigator.
- A light bandage and/or any physician recommended dressing may be applied post-evaluation.
- Any adverse events will be identified and documented.

4.9 30-Day Follow-up Visit (Visit 5)

- This visit may be performed in-office or as a telemedicine visit.
- Photographic images of each study lesion will be taken. Photographs are not required if the visit is not performed in-office.
- All lesions will be examined and clinically assessed by the site investigator. If the visit is not performed in-office, clinical assessment is not required.
- Any adverse events will be identified and documented. If the visit is not performed in office, the clinical site must inquire regarding any adverse events either by phone call, text, e-mail or video conference.

4.10 60-Day Follow-up Visit (BCC Surgical Excision Day – Visit 6)

- Photographic images of each study lesion will be taken.
- All lesions will be clinically assessed by the investigator.
- The site investigator shall assess each treatment area based on the Manchester Scar Scale

prior to excision.

- The site investigator shall complete the healing assessment questions for each treatment area prior to excision.
- Clinical measurements of the BCC lesion(s) shall be taken
- The site investigator shall complete the clinical lesion clearance assessment for each treatment area prior to excision.
- The subject shall assess each treatment area based on the SCAR-Q Appearance Scale prior to excision.
- A complete surgical tumor excision will be performed by the investigator with at least 5mm margins for each study lesion.
- The subject will be asked to rate his/her pain immediately after surgical excision by using a numerical rating score.
- All tissue shall be handled and shipped to the dermatopathology laboratory per the Tissue Handling and Analysis Procedure.
- Any adverse events will be identified and documented.

4.11 14-Day Post-Excision Follow-up Visit (Visit 7)

- Photographic images of each study area will be taken.
- Each study area will be clinically assessed by the investigator.
- Sutures shall be removed, as applicable.
- Photographic images of each study area will be taken post-suture removal.
- Any adverse events will be identified and documented.

4.12 30-Day Post-Excision Follow-up Visit (Visit 8)

- This visit may be performed in-office or may be performed as a telemedicine visit.
- Photographic images of each study area will be taken. Photographs are not required if the visit is not performed in-office.
- Each study area will be examined and clinically assessed by the site investigator. If the visit is not performed in-office, clinical assessment is not required.
- Any adverse events will be identified and documented. If the visit is not performed in office, the clinical site must inquire regarding any adverse events either by phone call, text, e-mail or video conference.

4.13 60-Day Post-Excision Follow-up Visit (Visit 9)

- Photographic images of each study area will be taken.
- Each study area will be clinically assessed by the site investigator.
- The site investigator shall assess each treatment area based on the Manchester Scar Scale.
- The site investigator shall complete the healing assessment questions for each treatment area.
- The subject shall assess each treatment area based on the SCAR-Q Appearance Scale.
- Any adverse events will be identified and documented.

4.14 Subject Withdrawal

A study subject has the right to discontinue participation at any time without penalty or loss of benefits to which the subject is otherwise entitled or may be withdrawn at any time at the discretion of the investigator for safety, behavioral, compliance, or administrative reasons. A withdrawn subject will be treated according to standard of medical care and will not be replaced.

If the participant withdraws consent for disclosure of future information, the sponsor may retain and continue to use any data collected before such a withdrawal of consent.

If a participant withdraws from the study, he/she may request destruction of any samples taken and not tested, and the investigator must document this in the site study records.

4.15 Discontinuation of CellFX Treatment Session

A participant may be discontinued from treatment with the CellFX System prior to completion of the entire treatment session in the event of intolerable pain or system failure of the CellFX System. If the study subject elects not to complete the treatment session, a study exit form shall be completed and documented as early termination. System failure of the CellFX System or component failure shall be documented on the Device Malfunction Form.

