3.2 Study Design

This study is designed as a prospective, multicenter IDE feasibility study in up to 30 adult participants with low-risk basal cell carcinoma utilizing the CellFX System at up to 6 sites within the United States. The study will consist of a single treatment session with the CellFX System followed by surgical tumor excision (with 5 mm margins) 60 days post-treatment.

Eligible subjects with 1-2 histologically confirmed, primary BCC lesion(s) who meet the inclusion and exclusion criteria will be enrolled. The BCC lesion(s) may be present anywhere on the body except neck, axilla, hands, feet, or genitals. In cases where the subject has more than 1-2 BCC lesions that meet the study criteria, the PI will select the lesion(s) to include in the study.

The subject will receive treatment of their confirmed BCC lesion(s) with the CellFX system. The treatment area will be evaluated at 3-days, 7-days, 14-days, 30-days and 60-days post-NPS treatment. At the 60-day follow-up visit, participants will undergo complete surgical excision of the tumor plus 5 mm margins. The subject will return for 3 more follow-up visits post-excision at 14 days (suture removal), 30 days and 60 days (typical skin check post-surgical excision) for a total of 9 study visits. The 3-day, 7-day, and 30-day post-NPS treatment follow-up visits as well as the 30-day post-surgical excision visit may be performed as telemedicine visits.

The excised tissue at the 60-day post-treatment visit will be shipped for histological analysis. Preparation and analysis of the excised tissue will be performed by Pinkus Dermatopathology Laboratory and a board certified dermatopathologist who has extensive experience in interpreting cutaneous neoplasms. Details of the preparation, shipment and analysis of the excised tissue are provided in the Tissue Handling and Analysis Procedure.

Photography of the study lesion(s) will be captured along with the investigator's assessments at all in-office visits. Detailed instructions for photography of the lesion area are provided in the photography instruction manual.

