3.6 Clinical Study Duration

It is anticipated that the enrollment of subjects in this study will take approximately 2-3 months in duration. All subjects included in this IDE feasibility study will return for follow-up visits at 3-days, 7-days, 14-days, 30-days, and 60-days post-NPS treatment. At the 60-day follow-up visit, participants will undergo complete surgical excision of the tumor plus 5 mm margins. The subject will return for 3 more follow-up visits at 14-days, 30-days, and 60-days post-excision for a total of 9 study visits. The total study duration will be 7 months.

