6.2 Analysis of the Primary Effectiveness Endpoint

The count and proportion with the primary endpoint of histological clearance will be calculated along with a 95% confidence interval (CI). The primary population for this analysis will be the Per-Protocol population, though estimates will be produced for the modified intent-to-treat/ safety population (patients who begin treatment) and Complete Treatment population (subjects who complete all required cycles of treatment).

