6.4 Safety Endpoints

Unless otherwise noted, the safety population will be used to assess safety endpoints.

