6.6 Populations for Analyses

The following populations are defined in Table 5.

Table 5. Population Descriptions for Analysis

Population	Description
Modified Intent-to-treat / Safety Population	All enrolled participants who began treatment with the CellFX system, irrespective of completed study treatment session, subsequent withdrawal, or deviation from the protocol.
Complete Treatment	This population consists of mITT participants who completed the entire CellFX treatment session.
Per-Protocol	Participants who received treatment, completed the CellFX treatment session, excision surgery and all required study visits.

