8.0 ADVERSE EVENTS

Pulse Biosciences will classify each reported Adverse Event according to ISO 14155:2011. All protocol specific AEs, whether device-related or not, will be recorded on the AE case report form and reported. Data to be collected will include the description of the AE, onset, and resolution dates (or whether the AE is ongoing), severity, management/treatment, outcome, and determination of the relationship to the device and/or procedure. All AEs related to the lesion site(s) should be reported and classified by the site Investigator and be followed by the Investigator to determine the relationship of the AE to the device or the study procedure.

All AE information will be collected from enrollment through the last study visit at 60 days following the surgical excision of the BCC lesion(s) (120 Days after the CellFX treatment session). All AEs will be followed until the event has resolved (in the case of permanent impairment, the event will be followed until it stabilizes, and the overall clinical outcome has been ascertained). Medical occurrences that begin before receiving a CellFX treatment but after obtaining informed consent will be recorded on the Medical History section of the CRF rather than the AE section.

When reporting AEs/SAEs, the Investigator should include the following information:

- Description of event
- Onset of event
- Duration of event (including resolution dates or whether the AE is ongoing)
- Severity
- Relationship to device or procedure
- Action taken
- Subject outcome

Severity describes the intensity of an event and will be assessed as:

- **Mild:** The AE does not interfere in a significant manner with the subject's normal functioning level.
- **Moderate:** The AE produces some impairment of function but not hazardous to health.
- **Severe:** The AE produces significant impairment of function or incapacities and/or it is a hazard to the subject.

Relationship to device or procedure will be assessed as:

- **Unlikely:** There is no indication that the AE was caused by the investigational or standard of care device.
- **Possibly:** It cannot be excluded that the AE was caused by the investigational or standard of care device.
- **Likely:** A causal relationship between the investigational or standard of care device and the AE is at least a reasonable possibility, i.e. there is evidence or argument suggesting a causal relationship.

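### Section 4.15 turns an elective stop of the CellFX session into a study exit, so treated subjects who stay in the mITT/safety population may have no Day 60 histology or scheduled AE follow-up

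*Combined protocol and SAP*

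**What the plan says.** Section 4.15 allows a session to be stopped early for intolerable pain or a system failure. For a subject who chooses to stop it says: "If the study subject elects not to complete the treatment session, a study exit form shall be completed and documented as early termination". A system or component failure goes on a malfunction form, and 4.15 does not say whether follow-up continues after it. It is equally silent on a pain stop decided by the investigator. Withdrawal from the study, by the subject or by the investigator, has its own section (4.14).

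The planned course is set out elsewhere. Section 3.6 states: "All subjects included in this IDE feasibility study will return for follow-up visits at 3-days", continuing to the Day 60 visit and excision. Section 8.0 states: "All AE information will be collected from enrollment through the last study visit at 60 days following the surgical excision", which is Day 120. Table 3 shows Study Exit only at Visit 9. Study histology comes from the Visit 6 excision; Section 3.2 says: "The excised tissue at the 60-day post-treatment visit will be shipped for histological analysis". Section 6.4.1 has investigators solicit adverse events at the scheduled visits.

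Table 5 defines the mITT/safety population as everyone who began treatment, "irrespective of completed study treatment session, subsequent withdrawal, or deviation from the protocol". Of the Complete Treatment set it says: "This population consists of mITT participants who completed the entire CellFX treatment session". Section 6.2 makes Per-Protocol the primary population for histological clearance and adds estimates in the other two. For safety, Section 6.4 says: "Unless otherwise noted, the safety population will be used to assess safety endpoints".

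**The concern.** Stopping a treatment and leaving a study are different events. A subject who cannot tolerate the rest of the session may be quite willing to return for visits and excision. Because 4.14 already deals with subjects who want to leave, the practical effect of the exit sentence in 4.15 falls on those who would have stayed.

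The subjects lost this way are not a random subset. They have been exposed to the device, at least some will have tolerated it poorly, and their lesions are only partly treated. They are the subjects in whom residual tumor and tolerability are of most interest, in a study whose stated purpose (1.6) is to find the optimal treatment and to design a pivotal trial. At stake are the meaning of the mITT clearance estimate and the completeness of the safety data.

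**Working it through.** **Step 1: what each estimate needs, and what 4.15 leaves.**

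| Estimate | Who is counted | Data needed | After an elective stop handled under 4.15 |
|---|---|---|---|
| Per-Protocol clearance (primary, 6.2) | Completed session, excision and all required visits | Visit 6 histology | Not in this population in any case |
| Complete Treatment clearance | Completed session | Visit 6 histology | Not in this population in any case |
| mITT clearance | Everyone who began treatment | Visit 6 histology | Counted, with no study histology |
| Primary safety (6.4, 6.4.1) | Everyone who began treatment | AEs solicited at visits to Day 120 | Counted, with no scheduled solicitation |

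Only the last two rows are affected.

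**Step 2: inputs for the size.** The plan gives no figure to reproduce: Section 6.5 sets a maximum of 30 participants and plans no hypothesis test. Assumptions for scale: 30 subjects, one lesion each, k elective exits without histology, and every other subject clear. The documents do not give k, so a range is shown. Intervals are exact (Clopper-Pearson) 95%. For n/n the lower limit is 0.025^(1/n); for 0/n the upper limit is 1 − 0.025^(1/n).

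**Step 3: mITT clearance.** If the exited subjects are left out, the estimate is (30 − k)/(30 − k). If all 30 are kept, the possible range runs from (30 − k)/30 to 30/30, a width of k/30.

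| k | Exits left out | Exits counted as not clear | Width of range |
|---|---|---|---|
| 0 | 30/30 (88.4–100%) | 30/30 (88.4–100%) | 0 |
| 1 | 29/29 (88.1–100%) | 29/30 = 96.7% (82.8–99.9%) | 3.3 points |
| 2 | 28/28 (87.7–100%) | 28/30 = 93.3% (77.9–99.2%) | 6.7 points |
| 3 | 27/27 (87.2–100%) | 27/30 = 90.0% (73.5–97.9%) | 10.0 points |
| 4 | 26/26 (86.8–100%) | 26/30 = 86.7% (69.3–96.2%) | 13.3 points |

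The upper end of the range is always 30/30 (88.4–100%). Section 6.2 does not say which way a subject without histology counts.

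**Step 4: safety.** Table 5 keeps the denominator at 30. With k = 2 and no event seen, the report is 0/30, upper limit 11.6%. Only 28 subjects were observed on schedule, and 0/28 has an upper limit of 12.3%. If one exited subject had a related serious event that the site never learned of, the true count would be 1/30 = 3.3% (0.1–17.2%).

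**The case against.** The strongest reply is that this is a wording ambiguity. Sections 3.6 and 8.0 and Table 3 describe the general course, and 4.14 to 4.16 describe departures from it; a specific exception does not contradict a general rule. Section 4.15 does not say that visits, excision or AE collection stop, and the sentence could be paperwork for the right to discontinue. All of this stands as far as it goes. But a study exit recorded as early termination is naturally read as the end of study visits, and nothing in 4.15 tells a site otherwise.

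A reader might infer three stronger things that the documents do not support.

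- *That 4.15 contradicts Table 5, 6.2 or 6.4.* It does not in wording. Table 5 expressly foresees incomplete sessions and withdrawals. The mismatch is that the population keeps subjects whose data collection 4.15 appears to end.
- *That the mITT estimate becomes identical to the Complete Treatment estimate.* That needs two further conditions: missing histology is dropped, and every incomplete session ends in exit. Section 6.2 does not state the first. The second fails for any system failure or investigator-decided stop that stays in follow-up, since the exit sentence covers only elective stops. With 30 kept in the denominator and k = 2, mITT would be 28/30 and Complete Treatment 28/28.
- *That harms go undetected or the cancer goes untreated.* Under 8.0, known events are followed until they resolve. Under 8.3, serious events and device effects that the site learns of are reportable within 3 calendar days. Standard care (4.14) and the promise of full care (5.3) make excision outside the study likely. What is lost is scheduled solicitation and study histology.

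It is also fair that 6.9 plans a tipping-point analysis for the Day 60 endpoints. This bounds the missing histology. It cannot recover it, and it does not restore AE visits.

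**Conclusion.** The point holds in a limited form. A stated rule would discard follow-up on subjects who have been exposed to the device and whom the analysis populations retain, and the loss would be informative.

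The effect is confined to the supplementary mITT clearance estimate, at up to 3.3 points of uncertainty per exit, and to the completeness of safety follow-up. The Per-Protocol primary estimate does not move, and no hypothesis test is at risk. The figures rest on 30 subjects with one lesion each, all others clear, and an assumed number of exits. If nobody elects to stop, there is no effect. The conclusion also rests on the natural reading of study exit and early termination, because 4.15 does not expressly cancel visits. The amendment is worth making because it is cheap and the data cannot be obtained afterwards.

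**What to change.** Amend 4.15 so that a stopped session is recorded as *session discontinued*, with its reason, separately from study exit. Complete the exit form at that point only if the subject withdraws, or is withdrawn by the investigator, under 4.14. Keep every other subject who began treatment on the scheduled visits, including after a system failure or an investigator-decided stop, with the Day 60 excision, study histology and AE follow-up to Day 120. The tipping-point analysis in 6.9 then covers whatever histology is still missing.

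The cost is a wording change and extra visits for a few subjects at most, possibly none. The mITT figures may come out slightly less favourable. Data from subjects who do withdraw under 4.14 are still lost. A partly treated lesion would wait until Day 60 for excision; Section 5.2 rates that delay as minimal risk, and 4.14 lets the subject withdraw, or the investigator withdraw the subject, for earlier standard care.
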